11.3.2 Secondary Outcome

Several secondary analyses that will further elucidate the efficacy of TAU+SCT, compared to TAU, for treating smokers in outpatient substance-abuse treatment for cocaine or methamphetamine dependence have been included in this study. For all repeated measures mixed model and generalized linear mixed model (GLMM) analyses, the response variable will be modeled using the appropriate link function. The effect of the intervention on change in response from baseline will be addressed by the treatment by week interaction parameter. Each model will adjust for possible site differences by including site as a random effect. The SAS procedure MIXED will be used for continuous variables, while GLIMMIX will be used for binary data. Before modeling is commenced, assumptions of linearity and covariance structure will be examined.

1. Stimulant-free/Drug-free UDS

GLMM analyses will be conducted to compare the percentage of TAU+SCT, relative to TAU, participants who have stimulant-free and drug-free UDS at the 3- and 6-month follow-up visits. Imputation methods used for the primary endpoint analysis will also be used for the 3- and 6-month models.

2. Drug-free Weeks

GLMM analysis will be conducted to compare the percentage of TAU+SCT, relative to TAU, participants who have drug-free weeks during the active treatment phase. Imputation methods used for the primary endpoint analysis will also be used for the analysis of drug-free weeks.

3. Stimulant-use and Substance-use Days

A repeated measures mixed model analysis will be conducted to compare the stimulant-use and substanceuse days reported during the active treatment phase as a function of treatment group. A mixed model analysis will also be conducted to compare the stimulant-use and substance-use days reported for the 28 days prior to the 3 and 6-month follow-up visits as a function of treatment group.

4. Ratio of treatment hours attended to hours scheduled

The ratio of the number of outpatient (including intensive outpatient) substance-abuse treatment hours attended to the number of hours scheduled during the active treatment phase will be analyzed using a GLMM

analysis with the log of the number of scheduled hours and the type of patient (intensive outpatient or outpatient) as covariates.

For a number of the remaining secondary outcomes, the effect of TAU+SCT, relative to TAU, is considered for both the active phase and follow-up phase. For these outcomes, a reference is made to controlling for baseline values. In the context of these analyses, the 'baseline value' for the active phase is the value of the outcome prior to randomization. If the analyses reveal a significant treatment effect during the active phase, then the 'baseline value' for the follow-up phase will be the outcome prior to randomization; this analysis will evaluate whether the effect observed during the active treatment phase is maintained through follow-up. If the analyses reveal no significant treatment effect during the active phase, then the 'baseline value' for the outcome measured at the end of the active phase; this analysis will evaluate whether a treatment effect becomes evident over a longer period of time (i.e., a "sleeper" effect).

5. The ASI- Lite

The seven areas of functioning measured by the ASI- Lite (medical status, employment status, drug use, alcohol use, family status, legal status, psychiatric status) will be assessed at baseline, the end of the active treatment phase and at the 3- and 6-month follow-up visits. These data will be analyzed using a repeated measures mixed model with group, time, time X group interaction and baseline values controlled as noted above. Significance of Group is declared if the joint effect of the Group and Group X time interaction (as defined by a change in log-likelihood) was significant (p<0.05). These 7 tests will be performed without adjustment for multiple testing.

6. Sexual Risky Behavior as assessed by the RAB

The sex risk scale of the RAB, which produces a score ranging from 0-28, will be assessed at baseline, the end of the active treatment phase and at the 3- and 6-month follow-up visits. The sex risk score data will be analyzed using a repeated measures mixed model with group, time, time X group interaction and baseline values controlled as noted above. Significance of Group is declared if the joint effect of the Group and Group X time interaction (as defined by a change in log-likelihood) is significant (p<0.05).

7. Cocaine/METH craving as assessed by the BSCS

The BSCS craving score, which ranges from 0-12, is assessed weekly during the active treatment phase and at the 3- and 6-month follow-up visits. These data will be analyzed using a repeated measures mixed model.

8. Smoking Point-Prevalence Abstinence

GLMM analyses including site and treatment group will be used to model rates of achieving point prevalence abstinence as assessed at the week 10 visit of the active treatment phase and at the 3- and 6- month follow-up visits.

9. Continuous Smoking Abstinence

GLMM analyses including site and treatment group will be used to model rates of achieving continuous smoking abstinence during post-quit days 15-42.

10. Cigarettes per Day (CPD)

Given the smoking quit date's likely substantial impact on CPD, analyses for CPD during the active treatment phase will be conducted for the pre-quit and post-quit phases as well as for the entire treatment phase, with the treatment x week interaction effect for study weeks 4-9 being the effect of interest. A

repeated measures mixed model analysis will be conducted to compare the CPD reported for the 28 days prior to the 3 and 6-month follow-up visits as a function of treatment group.

11. Participants with Continuous Smoking Abstinence

The primary outcome analysis will be modified to compare the percentage of participants who achieve continuous smoking abstinence, relative to those who do not, on stimulant-free weeks during study weeks 4-10 of the active treatment phase. In addition, GLMM analyses will also be conducted to compare the percentage of participants who achieve continuous smoking abstinence, relative to those who do not, on stimulant-free UDS at the 3- and 6-month follow-up visits.

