6.5.2 Secondary Outcome Measures

6.5.2.1 Drug-abuse Outcomes

The impact of TAU+SCT, relative to TAU, on drug-abuse outcomes will be evaluated with the following assessments:

1. Stimulant-free UDS Results at Follow-up

A UDS will be obtained at the 3- and 6-month post-quit follow-up visits. The treatment groups will be compared on the percentage of participants providing a stimulant-free UDS coupled with self-report of no illicit stimulant use at each of these visits.

2. Drug-free UDS Results

This outcome measure is the percentage of drug-free weeks/UDS results for three time-periods: the active treatment phase, and the 3- and 6-month post-quit follow-up visits. The outcome during the active treatment phase is the percentage of participants who are drug-free during each week, as assessed by qualitative UDS. A drug-free week is defined as a week in which both urine samples test negative for drugs of abuse and the participant self-reports no illicit drug use. A drug-positive week is defined as a week in which at least one urine sample tests positive for an illicit drug or during which the participant self-reports illicit drug use. Missing urine samples during the active treatment phase will be treated as described in section 11.3.1. At the 3- and 6-month post-quit follow-up visits the treatment groups will be compared on the percentage of participants providing a drug-free UDS coupled with self-report of no illicit drug use at each of these visits.

3. Timeline Follow-back (TLFB)

The Timeline Follow-back (TLFB) procedure (Sobell and Sobell, 1992; Fals-Stewart, 2000) will be used to assess the participants' self-reported use of substances for each day of the study. Outcomes derived from this assessment will include the number of stimulant-use days and the number of substance-use (i.e., alcohol and/or illicit use) days during the active treatment phase. Substance-use days is a key outcome measure in that abstinence from all substances, including alcohol, is the treatment goal for many CTPs and, thus, it is important to assess the degree to which participants achieve this abstinence goal. For the follow-up periods, stimulant-use and substance-use days will be assessed for the 28 days prior to the follow-up visit.

4. Substance-abuse Treatment Attendance

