11.3 Analysis Plan

Each primary and secondary efficacy outcome measure will be analyzed for the intent-to-treat (ITT) population. While there is every intention to be complete in describing the analyses to be performed, it is not possible to anticipate every contingency, and some adjustments may be required to meet constraints posed by the structure of the data. Constraints such as non-linearity, non-normality, etc. may lead to different but more appropriate approaches to analysis.

All statistical tests will be conducted at the 5% Type I error rate (two-sided). When multiple tests are conducted, the chance of finding a significant difference in one of the tests, when in fact no difference exists, is greater than the stated Type I error rate. The investigators are aware of the multiple testing issues and will interpret results with caution and use confidence intervals where possible.

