11.3.1 Primary Outcome

The primary hypothesis is that a significantly greater percentage of TAU+SCT, relative to TAU, participants will be stimulant-free during the weeks of the active treatment phase. For each participant, a stimulant-free week is defined as a week in which both urine samples test negative for stimulants and the participant self-reports no illicit stimulant use. A stimulant-positive week is defined as a week in which at least one urine sample tests positive for a stimulant or during which the participant self-reports illicit stimulant use. However, in the analysis of data from any clinical trial, strategies must be employed for handling missing data. In this trial, data for a week in which both urine samples are missing and the participant self-reports no illicit stimulant use will be treated as missing. For a week in which one stimulant-free UDS is produced, the second urine sample is missing, and the participant self-reports no illicit stimulant use or the self-report data are missing will be treated as negative (Table 6).

Data will be analyzed using a generalized linear mixed model (GLMM) for repeated-measures analysis (Brown and Prescott, 1999). Suppose Y represents the vector of observed response data, X and Z the fixed and random effects design matrices, and α and β be the vectors of fixed and random effects, respectively. Then, the GLMM model formulation assumes that

$$\mathrm{E}(\mathrm{Y}|\beta) = g^{-1}(\mathrm{X}\alpha + \mathrm{Z}\beta),$$

where $E(Y|\beta)$ is the expected value of Y conditional on the random effects vector, g^{-1} is the inverse link function, and $X\alpha + Z\beta$ is the linear predictor. The response variable Y will be modeled using the logit link function, i.e., $g(\mu) = \log(\mu / (1 - \mu))$. Fixed effects will include treatment group and week, while random effects will include site. SAS Proc GLIMMIX will be used to fit the model as follows:

proc glimmix; class site treatment; model Y = treatment week treatment*week / dist=binary link=logit covb solution; random intercept / subject=site; random _*residual_*/subject=patientid type=cs; run;

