The model formulation implies the same treatment effect in each site. The effect of the intervention on change in response from baseline will be addressed by the treatment by week interaction parameter. Due to the possibility that CTPs may differ in their success at helping participants become/remain stimulant-free, each regression model will adjust for site effects. Site will be included in the GLMM model as a random effect based on the participation of 12 CTPs. Assumptions of linearity will be examined by adding a restricted cubic spline to represent nonlinearity (Harrell, 2001). Assumptions for the covariance structure that provides the best fit to the data will be analyzed using the COVTEST statement under SAS Proc GLIMMIX. Since GLMM inference is only valid if data are missing at random (MAR), logistic regression analyses will be conducted to identify patterns of attrition and to determine if there is differential attrition by treatment condition. A binary indicator variable for missing data will be regressed on treatment assignment and other covariates. Variables that are associated with attrition at or below the α =0.10 level of significance will be included in subsequent analyses where the assumption of data missing at random (conditional on covariates) is required (Verbeke and Molenberghs, 2000).

If the random effects model unexpectedly fails to converge, then a general estimating equation (GEE) approach will be employed treating site as a fixed effect. If this model is utilized, then missing data (see Table 6) will be imputed using standard multiple imputation procedures, since GEE inference is only valid if data are missing completely at random (MCAR). SAS Proc MI will be used to create five complete data sets

using multiple imputation. Each data set subsequently be analyzed using SAS Proc GENMOD (the GEE procedure), and the results combined using SAS Proc MIANALYZE.

Urine Drug Screen - Stimulant result		Time Line Follow Back (TLFB)				
Result	Result	At least one positive day	All days negative	Some days negative, some missing	All days missing	
-	-	+	-	-	-	
+	-	+	+	+	+	
+	+	+	+	+	+	
+	0	+	+	+	+	
0	0	+	Missing	Missing	Missing	
_	0	+	-	-	-	

Table 6:	Stimulant-	use assignment	t for study	week as a	a function	of TLFB and	UDS result
			•				

Note: '0'=missing, '+'=positive and '-'=negative

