11.3.4 Missing Data

Logistic regression analyses will be conducted to identify patterns of attrition and to determine if there is differential attrition by treatment condition. A binary indicator variable for missing data will be regressed on treatment assignment and other covariates. Variables that are associated with attrition at or below the α =0.10 level of significance will be included in subsequent analyses where the assumption of data missing at random (conditional on covariates) is required.

For the primary outcome measure, whether (yes/no) a participant is stimulant-free during each week of the active treatment phase, missing data will be addressed as described in section 11.3.1. For the smoking outcome measures, missing smoking self-report/CO data will be treated as positive for smoking.

For all other outcome measures, and as a supplementary sensitivity analysis for the outcome measures above, a model to predict the existence of missing data based on the baseline covariates will be examined. Any baseline covariate that is related to the occurrence of missing data will be added to the list of control covariates for the hypothesis test. To minimize any impact of attrition on the test of hypotheses, intent-to-treat analyses will be conducted for all hypotheses. The GLMM analysis described in section 11.3.1 allows a missing at random assumption (Dang, Mazumdar and Houck, 2008). With these methods, if data are MAR, weeks with missing outcome may be ignored, and will therefore not be imputed. If the random effects model (GLMM) unexpectedly fails to converge, a general estimating equation (GEE) approach treating site as a fixed effect will be used. If this model is utilized, then missing data will be multiply imputed using standard multiple imputation procedures, since GEE inference is only valid if data are missing completely at random (MCAR).

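### The 3- and 6-month UDS models borrow an imputation method that the planned primary analysis does not have, leaving available-case analyses into which no active-phase results are stated to enter

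*Protocol*

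**What the plan says.** Protocol section 11.3 states that each primary and secondary efficacy outcome "will be analyzed for the intent-to-treat (ITT) population". Section 11.3.2, item 1, plans mixed-model comparisons of stimulant-free and drug-free UDS at the 3- and 6-month visits. It settles missing data by reference: "Imputation methods used for the primary endpoint analysis will also be used for the 3- and 6-month models".

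The primary analysis contains three things to which that reference might point:

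- **Planned mixed model.** Section 11.3.4: "if data are MAR, weeks with missing outcome may be ignored, and will therefore not be imputed".
- **GEE fallback, used only if the mixed model fails to converge.** Section 11.3.1: "If this model is utilized, then missing data (see Table 6) will be imputed using standard multiple imputation procedures", with the detail that "SAS Proc MI will be used to create five complete data sets".
- **Table 6 assignment rules.** These classify a study week from two urine results and the TLFB. A week without either urine stays unclassified unless the TLFB shows use: "data for a week in which both urine samples are missing and the participant self-reports no illicit stimulant use will be treated as missing".

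Follow-up is measured differently. Section 6.5.2.1 says "A UDS will be obtained at the 3- and 6-month post-quit follow-up visits", which is one sample per visit, read together with self-report.

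Sections 11.3.1 and 11.3.4 also regress a missingness indicator on treatment and other covariates, and carry forward those associated at the 0.10 level. Section 11.3.4 adds a missingness model on baseline covariates. For the outcomes with their own missing-data rule it serves as a supplementary sensitivity analysis.

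**The concern.** The reference looks like a missing-data method but supplies none on the path that the protocol expects to follow. Followed literally, a participant who attends neither follow-up visit contributes nothing to the test of the first secondary hypothesis, and one who attends a single visit contributes that visit.

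Ignoring missing weeks is easier to defend in the active phase, because a participant's other weeks are in the same model and carry information about the missing one. At follow-up the model has at most two results per person, and nothing is said to bring in the ten active-phase weeks. Those weeks are the best available predictor of later stimulant use and a likely predictor of attendance. The protocol itself links the two: Table 1 justifies exclusion 17 on the ground that heavy users are unlikely to complete. At stake is whether the longer-term comparison describes everyone randomized or is shifted by who returned.

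**Working it through.** **1. What the reference delivers.** The protocol gives no figure for follow-up attrition or for the follow-up comparison, so there is none to reproduce. Tracing the text:

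- Mixed model converges (planned path): no imputation.
- Mixed model fails: multiple imputation, with no statement on whether active-phase results enter the imputation model.
- Table 6: no row for a single UDS. A missed visit has neither urine nor self-report, which matches only the cell that remains missing.

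The planned follow-up analysis is therefore available-case.

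**2. Attrition that differs by arm only.** Take a true stimulant-free rate of 0.60 in both arms (the TAU assumption in section 11.4, applied to both arms so that there is no effect). If attendance is 85% in TAU and 70% in TAU+SCT, unrelated to use, the rate among attenders is

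- TAU: 0.6×0.85 / (0.6×0.85 + 0.4×0.85) = 0.60
- TAU+SCT: 0.6×0.70 / (0.6×0.70 + 0.4×0.70) = 0.60

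The bias is zero.

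**3. Attendance that also depends on active-phase use.** Assume a correlation of 0.488 between an active-phase result and the follow-up result. This is an assumption; the 0.65 in section 11.4 is a maximum used for sample size and does not address weeks 16 and 28.

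- P(free at both) = 0.36 + 0.488×0.24 = 0.477
- P(free at follow-up, given free earlier) = 0.477/0.6 = 0.795
- P(free at follow-up, given positive earlier) = (0.6 − 0.477)/0.4 = 0.3075

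Let attendance be 85% if free and 75% if positive in TAU, and 85% and 55% in TAU+SCT:

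- TAU attenders: (0.6×0.85×0.795 + 0.4×0.75×0.3075)/0.81 = 0.4977/0.81 = 0.614
- TAU+SCT attenders: (0.6×0.85×0.795 + 0.4×0.55×0.3075)/0.73 = 0.4731/0.73 = 0.648

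The false difference is 0.034. A simulation of the same set-up with 400,000 participants gave 0.615 against 0.650. Re-weighting each arm to its full active-phase distribution gives 0.6×0.795 + 0.4×0.3075 = 0.600 in both arms, so using the active-phase result removes the bias. With the same dependence and the same attrition in both arms (85% and 65%), the simulated rates were 0.631 and 0.629: no false difference, but both rates too high.

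**4. With the planned safeguard and exclusion 17.** This simulation uses a random-intercept logistic model with SD 4.24, which gives correlation 0.65 at a rate of 0.6. There is no true effect and there are 200,000 participants per arm. Missingness rises with active-phase use at assumed slopes. The adjustment is for all-negative against any-positive on three screening UDS, assumed to share the participant effect. Entries are TAU+SCT minus TAU, in percentage points.

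| Missing, TAU / TAU+SCT | Unadjusted | Adjusted for baseline UDS | Exclusion 17 applied, unadjusted | Exclusion 17 applied, adjusted |
|---|---|---|---|---|
| 22% / 14% | −4.2 | −1.6 | −1.7 | −1.1 |
| 30% / 14% | −9.0 | −3.7 | −3.5 | −1.8 |
| 14% / 27% | +7.9 | +3.4 | +3.1 | +1.6 |

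The missing percentages are those before exclusion 17; applying it lowers them at the same slopes. In a similar set-up, imputing within levels of active-phase use left at most 0.3 point.

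**5. Must the dependence itself differ by arm?** No. With the same log-odds dependence in both arms but 23% against 39% missing overall, the false difference was 4 to 5 points, 3 to 4 after stratifying on a baseline status, and at most 0.2 when active-phase results were used.

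**The case against.** The strongest reply has four parts.

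First, the sentence is not wholly empty: Table 6 and the GEE fallback are missing-data procedures, and the author may have meant to carry both over. That is fair, but neither fills a missed follow-up visit on the planned path.

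Second, the plan has a safeguard in its attrition-related covariates, and it matters: in the table it removes roughly half of the false difference or more before exclusion 17 is applied. It does not close the gap. The sensitivity model in section 11.3.4 is confined to baseline covariates, and the other covariates in section 11.3.1 are not named.

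Third, an available-data likelihood analysis under missing at random is compatible with an intent-to-treat population. That stands. A reader might infer that these are complete-case analyses that break intent-to-treat. The documents do not support that, because a participant with one attended visit can still contribute.

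Fourth, every attrition rate here is assumed, and model details may sit in an SAP that is not shown. The first is true and limits the claim to a range. The second does not rescue a rule that the protocol does state and that points to a method absent from its planned path.

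A reader might also infer that unequal attrition between arms is enough to bias the comparison. Step 2 shows that it is not.

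**Conclusion.** The point holds as a defect in the stated rule with a conditional consequence. Sections 11.3.2 and 11.3.4 do not fit together: the follow-up models are told to use imputation methods that the planned primary model does not have, and Table 6 does not map to a single UDS. What results is an available-case analysis under missing at random given treatment, site and any attrition-related covariates.

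Bias requires two conditions together: missing a visit depends on active-phase stimulant use, and either that dependence or overall attrition differs by arm. The exclusion 17 rationale makes the first plausible; nothing in the protocol establishes the second. Under the assumed rates the false difference is about 4 to 8 points unadjusted (9 in the widest scenario). After adjustment for baseline UDS it is about 1 to 4 points, with the low end when exclusion 17 is applied. For scale, the trial is powered for a 10-point difference (0.6 against 0.7) on the primary outcome. The direction cannot be determined in advance. This is a cheap improvement to a secondary analysis, not a demonstration that the planned result will be wrong.

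**What to change.** Replace the sentence in section 11.3.2, item 1, with an explicit follow-up rule:

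- **Main analysis.** Multiply impute missing week 16 and week 28 results from treatment, site, baseline UDS stratum and the active-phase weekly results. Alternatively, fit one longitudinal model to weeks 1–10, 16 and 28 and take the treatment contrasts at weeks 16 and 28. Either is preferable to adding active-phase use as an ordinary covariate in the outcome model, since it is measured after randomization and may carry part of the treatment effect.
- **Assignment rule.** State how Table 6 applies to one UDS plus TLFB, including an attended visit with a missing urine.
- **Sensitivity analysis.** Keep the available-case mixed model and report it beside the main result.

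This corrects for attrition that the active-phase results explain, but not for attrition driven by unobserved use at follow-up.

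The cost is a wording change and a little more programming. The data are already collected, and Proc MI and Proc MIANALYZE are already planned for the fallback.

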11.4 Sample Size Estimate

The minimum sample size required to achieve 80% power using an alpha level of 0.05 (two-sided) and a 1:1 randomization ratio was computed based on a repeated measures study design that takes into account that the data are binary and can be correlated across repeated measurements (Rochon, 1998). We assumed a compound symmetry covariance structure to be conservative (correlation between 2 successive time points does not change over time), as well as a maximum correlation between any 2 time points of 0.65. The higher the assumed correlation between time points, referred to as phi, the less information that we gain from successive measurements, thus requiring a larger sample size. The assumption of 0.65 for the present study is based on the phi calculated for the stimulant UDS results from the subgroup of cocaine dependent participants in CTN-0009, a study that evaluated the impact of concurrently providing smoking-cessation treatment with substance-abuse treatment.

The probability of stimulant-free urines in the TAU group is another key assumption in determining sample size. A review of the stimulant UDS results for cocaine-dependent participants from three prior CTN studies, CTN-0009, CTN-0015 (Seeking Safety for women with PTSD and substance-use disorders), and CTN-0006 (Contingency management for stimulant abusers) produced probabilities ranging from 0.55 to 0.75, with the lower probabilities (i.e., 0.55) requiring larger sample sizes. Based on these prior studies, we assumed a probability of 0.6 for stimulant-free urines in the TAU group. A final key consideration in calculating sample size is the size of the group difference to be detected. The present study has been powered to detect the lower limit of a clinically meaningful effect. Specifically, this study will detect a group difference if the probability of stimulant-free urines in the TAU+SCT group is at least 0.7.

The sample size yielded from the assumptions outlined above is 528, with 264 in each treatment group. As described in section 11.6, an interim analysis to evaluate the accuracy of the assumptions made in calculating this sample size will be conducted, with an adjustment made to the sample size if needed.

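### Follow-up models for use days and cigarettes per day name no baseline term, and baseline's role is undefined for active-phase use days and craving, at a cost in precision

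*Protocol*

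**What the plan says.** All references are to the protocol.

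- **Use days (11.3.2, item 3).** The active-phase comparison is a repeated measures mixed model by treatment group. The follow-up comparison takes the "days reported for the 28 days prior to the 3 and 6-month follow-up visits as a function of treatment group". No baseline covariate is named in either.
- **Craving (item 7).** BSCS is described as assessed weekly in the active phase and at both follow-up visits, then: "These data will be analyzed using a repeated measures mixed model". Baseline is not listed among the data, and no covariate is named.
- **CPD at follow-up (item 10).** A "repeated measures mixed model analysis will be conducted to compare the CPD reported for the 28 days" before each follow-up visit, by treatment group.
- **ASI-Lite and RAB (items 5 and 6).** Both list baseline among the assessments and are modelled with "baseline values controlled as noted above".
- **Rule on baseline values (paragraph before item 5).** It covers some of the outcomes that follow it, namely those whose text refers to baseline control. The pre-randomization value is used in the active phase. At follow-up it is kept only if the active-phase effect was significant; otherwise the end-of-active-phase value replaces it.
- **General statement (opening of 11.3.2).** For the secondary mixed models, treatment-by-week is said to address the effect on change from baseline.
- **Data available (Table 2).** TLFB and BSCS are both marked once at screening/baseline.

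**The concern.** Earlier drug use, craving and smoking rate usually predict later values of the same measure. A model that uses the baseline value removes that share of the outcome variance and corrects chance differences between the arms. The protocol does this for ASI-Lite and RAB but does not state it for use days, follow-up CPD or craving. Substance-use days is described in section 6.5.2.1 as a key outcome, so its comparison should not be less precise than that of the ASI-Lite.

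There is also a mismatch for craving. The active-phase hypothesis in 11.1.2 is a greater reduction from baseline. If the model holds only post-randomization scores and no baseline covariate, treatment-by-week tests whether the trends after randomization differ, which is a different question.

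**Working it through.** **1. Is a baseline value in each model as written?**

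| Outcome | Baseline collected (Table 2) | Baseline in the model text |
|---|---|---|
| ASI-Lite, RAB (items 5, 6) | yes | yes, controlled |
| Use days, follow-up (item 3) | yes (TLFB) | no; treatment group only |
| CPD, follow-up (item 10) | yes (TLFB) | no; treatment group only |
| Use days, active phase (item 3) | yes (TLFB) | unclear; general treatment-by-week statement only |
| BSCS (item 7) | yes | unclear; general treatment-by-week statement only |

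The rule on baseline values comes after item 3 and is confined to later outcomes, so it does not reach use days. Items 7 and 10 do not invoke it. At follow-up, the data described in items 3 and 10 are the two 28-day windows, so the general statement has no baseline observation to act on. Elsewhere the protocol is explicit when baseline belongs to the response series: the vital signs, HADS and PSQI models in 11.3.3 run from screening/baseline to week 10.

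**2. The plan's own figure.** The protocol states no power for these outcomes. Its only sample size, 528, is for the binary primary outcome. From 0.6 versus 0.7, 80% power, two-sided 0.05 and "a maximum correlation between any 2 time points of 0.65" (section 11.4), a single measurement needs 356 per arm, or 376 with continuity correction. Ten weeks under compound symmetry give the factor (1 + 9 × 0.65)/10 = 0.685. Then 356 × 0.685 = 243.9, so 488 in total; 376 × 0.685 = 257.6, so 516, within 3% of 528. The number of repeated measurements used is not stated. Nothing below depends on 528 being right.

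**3. Precision gained by adjustment, one follow-up time point.** Inputs: two-sided 0.05 (section 11.3), and a reference effect that has 80% power unadjusted. The baseline-outcome correlation r is assumed. Adjustment multiplies the variance by 1 − r², so

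power = Φ[(0.842 + 1.960)/√(1 − r²) − 1.960].

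| r (assumed) | 1 − r² | Power after adjustment |
|---|---|---|
| 0.2 | 0.96 | 81.6% |
| 0.3 | 0.91 | 83.6% |
| 0.5 | 0.75 | 89.9% |
| 0.7 | 0.51 | 97.5% |

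With 264 per arm and complete data, the detectable difference at 80% power is 2.802 × √(2/264) = 0.244 SD unadjusted. Multiplied by √(1 − r²), it becomes 0.239, 0.233, 0.211 and 0.174 SD.

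**4. Mean of the two follow-up visits.** With one common correlation r among baseline and both visits, the variance is (1 + r)/2 unadjusted and (1 + r)/2 − r² adjusted.

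| r (assumed) | Unadjusted | Adjusted | Ratio | Power after adjustment |
|---|---|---|---|---|
| 0.2 | 0.60 | 0.56 | 0.933 | 82.6% |
| 0.3 | 0.65 | 0.56 | 0.862 | 85.5% |
| 0.5 | 0.75 | 0.50 | 0.667 | 92.9% |
| 0.7 | 0.85 | 0.36 | 0.424 | 99.0% |

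Under this assumption the gain is somewhat larger than at a single visit.

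**The case against.** **Silence is not exclusion.** Covariate lists for secondary models are often left to the statistical analysis plan, which is not at hand, and section 11.3.4 refers to control covariates that 11.3.2 does not list for each item. This has weight, but the protocol did not leave the matter open: it names baseline control item by item and does so unevenly. Section 11.3.4 adds a baseline covariate only if it is related to missingness, which is a different criterion from being prognostic.

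**Craving and active-phase use days may already use baseline.** A reader might infer that these models leave baseline out. The text does not support that. The general treatment-by-week statement, and a craving hypothesis framed as reduction from baseline, are compatible with a week-0 response. What can be said is that the role of baseline is undefined there.

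**No bias follows.** A reader might also infer that the comparisons are invalid or seriously exposed to imbalance. Randomization protects them, and stratification by baseline stimulant UDS (section 6.6) partly limits imbalance in stimulant use, though not directly in craving or CPD.

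**The size is hypothetical.** It is tempting to convert the gain into participants, for example 528/0.75 = 704 at r = 0.5. That attaches the primary outcome's sample size to outcomes with no stated power. The correlation of 0.65 concerns weekly stimulant UDS and cannot be carried over as fact. At r = 0.2 the single-visit gain is under 2 percentage points.

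**The comparator is itself uneven.** ASI-Lite and RAB may switch to the end-of-active-phase value at follow-up, so copying their rule would not give a consistent pre-randomization adjustment. This stands, and the fix allows for it.

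**Conclusion.** The point holds in full for the follow-up models of stimulant-use days, substance-use days and CPD: they are specified by treatment group alone although a baseline TLFB is taken. For active-phase use days and BSCS it holds as a lack of definition, since the protocol claims to address change from baseline without placing a baseline value in the model.

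The consequence is lost precision and inconsistency between items, not invalid inference, and the primary analysis is untouched. Relative to 80% unadjusted power, the single-visit gain runs from about 2 points (r = 0.2) to about 17 points (r = 0.7). That range rests on an assumed correlation, an approximately normal treatment estimate, equal variances in the two arms and a linear relation with baseline. The gain applies to comparisons of level; a baseline main effect sharpens a treatment-by-week slope contrast less. This is a worthwhile improvement to secondary analyses rather than a condition for the trial's validity.

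**What to change.** In section 11.3.2:

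- **Items 3 and 10, follow-up models:** add the pre-randomization value of the same measure as a fixed covariate. For use days, express it as a rate over a defined baseline look-back; for CPD, use baseline CPD.
- **Item 7, and item 3 in the active phase:** enter the pre-randomization value as a covariate, or as a week-0 response with a baseline mean common to both arms, and say which.
- **Throughout these items:** use the pre-randomization value, not the end-of-treatment value that the rule before item 5 substitutes when the active-phase effect is not significant. The substituted value is measured after randomization, so conditioning on it changes the question. State how this relates to the rule kept for ASI-Lite and RAB.
- **TLFB:** state the baseline look-back window. The protocol does not give it, so a count matching the 28-day follow-up window cannot be assumed.

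The cost is one term per model and a short definition. TLFB and BSCS are already scheduled at screening/baseline, so no visits or participants are added. The change should be made before outcome data by arm are seen.
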